However there is a key difference in the clinical populations found in the literature, surgeons have an operative team and are not responsible for patient monitoring while operating. Likewise anaesthetists are usually accompanied by an ODP and are not undertaking practical skills in isolation.

We were not able to find any published literature addressing attention and perception during ICU procedures.

What does this research add?

There is no published experimental data investigating how clinician time perception and attention are impacted by performing tasks in an IC environment. There is an expectation that time perception and attention are preserved, such that clinicians can insert central access as a sole practitioner. Should our investigation show that attention is impacted then this could inform changes to practice as to how monitors and/or additional staff members are utilised during procedures and clinical tasks and how practitioners are trained to undertake them.

AIM(S) OF STUDY

- To investigate the relationship between task type, perceptual loading and attention in an ICU environment
- To investigate the relationship between task type, perceptual loading and time perception in an ICU environment
- To examine if the extent of these effects (if any) are affected by clinician role and/or experience

OBJECTIVES

The objective of this study is to measure clinician awareness of time progression and monitoring trends in the clinical environment during 2 different types of task.

HYPOTHESIS

H₀: Task type has no impact on clinician time perception or awareness of monitoring trends.

H_A: In the technical task clinician time awareness is more inaccurate than in the administrative task

H_B: In the technical task clinician awareness of monitoring trends is impaired compared to in the administrative task

STUDY DESIGN

STUDY SETTING/LOCATION

This will be a single-centre study undertaken in the Intensive Care Units at Great Ormond Street Hospital. The study tasks will be run in the simulation room on the general Paediatric ICU.

STUDY POPULATION

Participants will be recruited from the group of ICU junior/senior tier fellows and Consultants working on the ICUs at Great Ormond Street Hospital. This comprises a pool of around 40 staff members. All staff members are routinely involved in the care of patients in a PIC environment.

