Participants will be recruited through convenience sampling of those working or training on the ICUs on days when it is possible to run the tasks. Individuals will not be recruited more than once.

Each participant will be given a numeric study ID and parameters recorded against this including:

- Job title- Consultant/fellow
- Gender- Male/female/prefer not to say
- Age- 21-30/31-40/41-50/51-60/61+
- Number of CVCs that they have previously inserted - <10, 10-50, >50).
- Time since last simulation training- 1 week/ 2-4 weeks/ 1-2 months / 3-6 months / 7-12 months / 1-2 years / >3 years

STUDY OUTCOMES

Primary Outcomes

Mean and standard deviation (accuracy) of time intervals measured.

Accuracy of retrospective recall of trends in monitored observations.

Secondary Outcomes

Impact of experience on time perception and monitoring changes.

STUDY PROCEDURES

Recruitment of participants

Participants will be provided with the information sheet appended and given the opportunity to ask any questions before consenting to the study. They will be asked to sign the appended consent form. Their consent forms will be in no way linked to the data collected such that participants could be identified from their data.

Randomisation

Block randomisation will be used to ensure even distribution of individuals at each grade of experience between the allocation groups. A block size of 4 will be used with 2 strata (grade= Consultant, Other). The randomisation list was determined by an online randomisation service ^[27]. The list generated is included as an appendix.

Two parts of the experimental process are randomised.

The first is the order in which the administrative and technical tasks are performed- this is randomised to remove the impact of primacy-recency impacts as well as task training through more practice with the timing apparatus.

The second is the scenario displayed on the monitor. As we are asking participants to identify a trend, randomisation to an increasing or decreasing trend reduces the likelihood of guessing the correct answer.

The study cannot be blinded at the time of data capture given the significant obvious differences between the tasks.

Study procedure

Structure

The overall structure is outlined below with further detail on each section provided in the following section.

Section order	Comment
Consent and discussion	To ensure valid consent and answer queries

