All equipment laid out on a table. The tissue pad is attached to the mannequin leg and surgically draped appropriately. The ultrasound probe is already in a sterile sheath, lying on the sterile field.

Instructions to subject

You are the fellow/consultant looking after Sophie. Sophie is a 2 year old girl with PIMS-TS. She is intubated and is stable on minimal ventilation and peripheral noradrenaline of 0.1mcg/kg/min. She has just been admitted to the unit. This is Sophie's bedspace, all the equipment you see is part of the simulation.

Your task is to request the admission investigations according to the sheet provided.

The nurse looking after the patient has had to step out of the bedspace to prepare their infusions and have asked you to complete your task whilst keeping an eye on the patient in the bedspace.

I am the nurse in the next bedspace, if at any point you want to make a clinical intervention please continue with the task and verbalise anything you would like me to do.

As before, when I ask you to begin, please press the foot pedal every 10 seconds, trying to be as accurate as possible. The task will last for several minutes.

Events during the task:

If this task is the first task undertaken, then the bedside monitor will display the same values throughout, aside from 1 desaturation. Heart rate: 125 bpm, blood pressure: 90/50 (65), respiratory rate: 25, oxygen saturations: 98%, end tidal CO₂: 4.5 mmHg. The oxygen saturation measure will fall to 88% for 5 seconds at 30 seconds into the task, triggering an alarm. This is to orient the participant to the monitor being part of the environment.

Normal values for age are: Heart rate: 80-140 bpm, respiration rate: 20-28 (APLS), 5th centile systolic: $65+(2 \times 2)=69$, 5th centile MAP: $50+(2 \times 2)=54$.

At 30 seconds into the task there will be a 10 second desaturation to 88% with spontaneous normalisation to 98%.

If this is the second task undertaken then values on the monitor will change during the task.

There are 2 monitor scenarios, 'A' and 'B'. Allocation between these is determined in the randomisation table (see appendix). They are identical apart from 'A' being a falling trend and 'B' a rising trend

- Scenario A
 - The oxygen saturation measure will fall to 88% for 5 seconds at 30 seconds into the task, triggering an alarm. This is to orient the participant to the monitor being part of the environment.

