 - Correct identification of no trends in other parameters - reported as proportion of participants correct
 - Accuracy of magnitude recall
 - The blood pressure either falls or rises between a systolic/diastolic (mean) of 70/48 (55) and 90/50 (65).
 - From the position of the x on the linear blood pressure scales we can derive:
 - The accuracy of the initial and final estimates compared with the actual values- reported for each task as the population mean and standard deviation of the percentage errors compared with the actual value.
 - The accuracy of the magnitude of the change, determined through comparing the difference in the estimated initial and final values compared with the actual 20mmHg systolic/ 10mmHg diastolic change for each task. The population mean and standard deviation of the percentage errors compared with the actual change will be reported for each task.
 - We hypothesised that there would be a priming effect following administration of the questionnaire, with participants more likely to attend to blood pressure trends if the questions were asked prior to the second task. We will therefore only ask the questions after the second task. We can then compare between the subgroups, split by which of the tasks was performed second to examine the impact of task type.
 - i.e the questionnaire analysis will have half the n of the overall study
- For the above we can compare subgroups using Fishers exact test.
 - By task order
 - By grade
 - By number of CVCs previously inserted

- By first 25% vs last 25% of participants

STATISTICAL CONSIDERATIONS AND DATA ANALYSIS

Sample size and statistical power

This is a pilot study and as such we do not expect it to be adequately powered to confirm hypotheses but intend that it should be hypothesis generating.

Statistical methods

The population summary statistics detailed above will be calculated using 'SPSS statistics' software with built-in min/max/mean/IQR/SD calculation.

With assumed normally distributed timing data and each participant completing 2 tasks the distributions will be compared with a paired sample t-test for; control vs administrative, control vs technical and administrative vs technical. For subgroup analysis paired or unpaired sample t-tests will be used as appropriate in each case. For the trend perception outcomes, contingency tables will be created for each subgroup and compared using Fishers exact test.

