Appendix

Administrative task- instructions and task material

Instructions

You are the admitting doctor for a newly arrived patient.

Please request the admission PIM-TS investigations as on the sheet provided.

Investigations required

Sophie Digby

432 458 6644

14/8/2019

NKDA

Weight: 12kg

Investigations all to be completed within 24 hours, you carry bleep 1234:

- FBC
- UE, Bone, LFT, GGT, Mg
- LFTs, CRP, ESR, ASOT, Vitamin D, PTH
- Coagulation profile-not on anticoagulation, Group & Save
- Blood film
- D-Dimers, Ferritin, Immunology save serum, Triglycerides, LDH, CK
- Trop-I, NT-proBNP
- Amylase, Lipase, faecal calprotectin, urine albumin:creatinine ratio
- ECHO- Discussed with [name], Reason: Other
- Chest X-ray, AXR, Abdominal USS, EEG
- Diagcore SARS-CoV-2
- Respiratory Viral screen
- COVID serology
- Stool M,C&S, Stool enteric virus panel, and stool SARS-CoV-2 PCR
- Blood M,C&S, urine M,C&S, BAL M,C&S, throat culture
- Viral Blood PCR: EBV, CMV, Adeno, Enterovirus, HIV
- Blood PCR: Pneumococ., Meningococ., Group A strep, Staph A
- Lymphocyte subsets (TBNK)

Post task questionnaire

1. Overall the blood pressure:

Rose [] Stayed the same [] Fell [] I don't recall []

2. Overall the heart rate:

Rose [] Stayed the same [] Fell [] I don't recall []

3. Overall the respiratory rate:

[figure not shown]
Rose [] Stayed the same [] Fell [] I don't recall []

4. Mark the initial systolic blood pressure on the line below (with an x):

[figure not shown]
I do not recall the value []

5. Mark the initial mean blood pressure on the line below (with an x):

I do not recall the value []

6. Mark the final systolic blood pressure on the line below (with an x):

I do not recall the value []

7. Mark the final mean blood pressure on the line below (with an x):

I do not recall the value []

Randomisation list^[27]

Block sizes: 4

Stratification factors: Role (Consultant, Other)

Participant number	Monitor scenario	Role	
		Consultant	Other
1	A	Administrative first	Administrative first
2	B	Administrative first	Technical first
3	A	Technical first	Technical first
4	B	Technical first	Administrative first
5	A	Administrative first	Administrative first
6	B	Technical first	Administrative first
7	A	Administrative first	Technical first
8	B	Technical first	Technical first
9	A	Administrative first	Administrative first
10	B	Technical first	Technical first
11	A	Technical first	Technical first
12	B	Administrative first	Administrative first

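### The task-order list is printed in the protocol with fixed blocks of 4 and no concealment, which exposes the between-participant trend-awareness comparison; separately, the monitor scenario alternates instead of being randomised

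*Combined protocol and SAP*

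**What the plan says.** The Randomisation section sets the method: "A block size of 4 will be used with 2 strata (grade= Consultant, Other"). It adds that "The list generated is included as an appendix". Two things are said to be randomised: the order of the administrative and technical tasks, and whether the blood pressure trend on the monitor falls (scenario A) or rises (scenario B). The stated reason for the second is to make the right answer harder to guess.

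The Appendix prints the whole list, under the line "Stratification factors: Role (Consultant, Other"). It has 20 rows, one scenario column shared by both roles, and one task-order column per role. The events listed for the administrative task confirm that the scenario comes from the same place: "Allocation between these is determined in the randomisation table (see appendix").

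On recruitment, the Study Population section says "This comprises a pool of around 40 staff members" and "Participants will be recruited through convenience sampling of those working or training on the ICUs on days when it is possible to run the tasks".

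On analysis, the blood pressure changes only in the second task. The monitor trend perception analysis therefore compares subgroups "split by which of the tasks was performed second to examine the impact of task type".

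No section mentions sealed envelopes, central or third-party allocation, or any limit on who may see the list.

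**The concern.** A crossover of task order usually makes allocation concealment a minor matter, because each participant is their own control. That holds for the paired timing comparison. It does not hold for trend awareness, which is one of the two primary outcomes and the test of H_B. Each participant contributes one trend result, from one task, so the analysis is in effect a parallel-group comparison of those who did the technical task second with those who did the administrative task second. Its validity depends on the next order being unknown when a colleague is approached.

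The protocol's own premise gives selection something to act on. It says that load from a given task varies with skill and experience. The only stratum is Consultant versus Other, so junior and senior fellows share a stratum, and prior CVC experience is recorded but not balanced. In a single unit, whoever recruits is likely to know which colleagues are practised. Choosing, even without intent, who fills the next row could make the two order groups differ in ways that look like an effect of task type.

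The scenario raises a smaller, separate point. An alternating column is systematic allocation. Once one participant's scenario and position are known, the rest of the column follows, which weakens the safeguard against guessing.

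**Working it through.** **Inputs.** Fixed block size 4 and two strata (Randomisation section and Appendix); the 20 printed rows (Appendix); a pool of about 40 (Study Population). The protocol states no sample size or power figure, and none is needed here.

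**1. Reproducing the block size.** With A = administrative first and T = technical first, the printed orders in consecutive fours are:

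- Consultant: AATT, ATAT, ATTA, TATA, ATAT
- Other: ATTA, AATT, ATTA, TTAA, TTAA

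All 10 blocks contain two A and two T, so each role has 10:10 over 20 rows. The stated block size is confirmed.

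**2. Foresight with the list.** 2 roles × 20 rows = 40 allocations. All 40 orders and all 40 scenarios can be read in advance.

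**3. Foresight without the list, knowing only block size 4 and past orders.**

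- Theory: six arrangements are equally likely. The fourth order is always determined, and the third is determined in 2 of 6 arrangements (AATT, TTAA). Share certain = (1 + 1/3)/4 = 33%.
- This list: a block of the AATT or TTAA kind gives 2 certain orders and any other block gives 1. Consultant: 1×2 + 4×1 = 6. Other: 3×2 + 2×1 = 8. Total 14/40 = 35%.
- Guessing the under-represented order, with ties counted as 1/2: an AATT or TTAA block yields 2.5 correct and any other block 3. Theory: (2×2.5 + 4×3)/6 = 17/6 per block, or 70.8%. This list: Consultant 2.5 + 4×3 = 14.5; Other 3×2.5 + 2×3 = 13.5; total 28/40 = 70%. Unpredictable allocation gives 50%.

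**4. Would larger blocks solve it?** For a known block size 2m, expected correct guesses per block are m + [4^m / C(2m, m) − 1]/2.

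- m = 2: 2 + (16/6 − 1)/2 = 2.833, or 70.8%
- m = 3: 3 + (64/20 − 1)/2 = 4.1, or 68.3%
- m = 4: 4 + (256/70 − 1)/2 = 5.329, or 66.6%

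Sizes 6 and 8 are assumptions for illustration. A larger known block barely helps; hiding the list matters far more.

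**5. The scenario column.** Rows 1 to 20 read A, B, A, B without exception. Five random permuted blocks of 4 would alternate strictly with probability 2 × (1/6)^5 = 0.00026, and 20 independent fair draws with probability 2/2^20 = 0.0000019. The column does not look like a random draw.

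**6. Is scenario confounded with order?** Counts of scenario A/B:

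| Role | Administrative first | Technical first |
|---|---|---|
| Consultant | 6/4 | 4/6 |
| Other | 5/5 | 5/5 |
| Total | 11/9 | 9/11 |

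The imbalance is small.

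**7. What one placement is worth.** This assumes all 40 slots are filled, giving 20 per order group. One participant is then 1/20 = 5 percentage points of a group's proportion. Exchanging one person who would notice the trend for one who would not moves the groups in opposite directions, so the difference shifts by 2/20 = 10 points. This shows sensitivity only; nothing in the documents says that it happens.

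**The case against.** Several points on the other side are sound.

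- **Participants.** A reader might infer that staff taking part can foresee their own order or trend. The documents do not support that. Participants receive an information sheet and consent form; nothing says they see the protocol, the list or their row number. A participant who did hold the protocol would also have the hypotheses, the monitor values and the questionnaire, so removing the appendix alone would not close that leak.
- **Scenario and H_B.** A reader might infer that alternation itself biases H_B. No planned comparison is by scenario, and scenario is close to balanced across order. For a participant who cannot see the sequence, alternation still serves its purpose against guessing.
- **Scope for selection.** Stratification stops Consultants being shifted against Others. With 40 printed slots and a pool of about 40, selection may be more about who takes which row than who enters, and days on duty limit it further. No preference for an order is documented.
- **Size.** The 100% and 33% figures measure predictability. A reader might take them as an amount of bias; they are not.
- **Status.** The study is declared a hypothesis-generating pilot.

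Two possible defences do not answer the point. The structure table places randomisation after consent, but a list fixed in advance can be read before anyone is approached. The statement that "The study cannot be blinded at the time of data capture given the significant obvious differences between the tasks" concerns blinding during the task; concealing the next allocation beforehand remains entirely possible.

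**Conclusion.** The point holds in a limited form. The study team can foresee every task order, and no concealment is described. That leaves the H_B comparison open to selection within role strata. The paired timing comparison is little exposed. The scenario is called randomised but is allocated systematically; this is a discrepancy to correct, with no demonstrated effect on H_B.

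The amount of bias cannot be estimated from the documents, and no steering of recruitment is shown. Because this is a pilot, the matter is a worthwhile inexpensive improvement and does not invalidate the design.

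The conclusion assumes that the study team does the recruiting and holds the list; the protocol names nobody else for either role. The count of 40 allocations and the balance within blocks assume that the participant number counts within role, which the Appendix does not state. The list is foreseeable under either numbering.

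**What to change.** 1. Generate a new list for each role in which scenario is truly randomised and balanced within task order. For example, a block of 4 can hold each of the four order-by-scenario combinations once, in random sequence; 20 rows per role then give 20/4 = 5 of each combination.
2. Keep the list out of the protocol. Describe only the method, and state whether numbering runs within role.
3. Reveal each allocation only after consent and enrolment, for example by sequentially numbered sealed envelopes or through the online service, with the list held by someone who does not recruit.
4. As a secondary measure, use undisclosed, varied block sizes (multiples of 4 if the scheme in item 1 is used).
5. If recruitment has started, apply this to the remaining allocations and report the open list as a limitation of the trend-awareness comparison.

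Generating the list takes minutes; the rest is a short protocol edit and a set of envelopes or equivalent. Tasks, outcomes and sample size do not change. The one statistical cost is slightly looser balance if recruitment stops partway through a larger block.

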Randomisation	Randomisation of task order and monitor trend scenario: increasing/decreasing
Timing control task	To assess baseline time perception for each participant
Break	To reset and brief the participant for the first task
First task	Administrative or technical task depending on randomisation

Monitor scenario in first task	The parameters do not change aside from a brief desaturation at 30 seconds into the task, to orient participants to the monitor within the task
Break	To reset and brief the participant for the second task
Second task	Administrative or technical task depending on randomisation
Monitor scenario in second task	There is a desaturation at 30 seconds as before to orient participants to the monitor within the task. The blood pressure then either falls or rises, depending on the randomisation, settling at the final value at 4 minutes. The change in blood pressure only occurs in the second task so as to allow immediate review of trend awareness, this is not possible to do after the first task without introducing bias in the second task.
Post task review	To check immediate recall of monitor trends in the second task. Asked immediately to reduce the impact of recall/memory bias on the answers.
Questionnaire	Provides quantification of any trend in parameters noticed.
Debrief	To answer queries and identify any areas of participant support required.

Experimental scenarios:

Each participant will undertake the timing control task first and then both the administrative and technical tasks, the order of these determined by the randomisation table.

1. Timing control

The participant sits and is asked to push a foot pedal every 10 seconds with no reference to external timekeeping. This task continues for 6 minutes.

Participants are instructed: "Please press the foot pedal every 10 seconds, trying to be as accurate as possible. The task will last for several minutes."

After 6 minutes the participant will be asked for the time period they believe has elapsed between the first pedal press and the last.

2. Administrative task:

Request investigations for a new admission

Equipment required:

- PIMS-TS investigations pack
- Computer signed in to the EPIC learning environment for a dummy patient
- Simulated bedside monitor
 - Varies observations over time in line with preset programming determined by the study team
- Foot pedal and data recorder for time logging

Setup

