 - The trend in monitored observations- increasing or decreasing blood pressure in the second task

The following parameters are measured during both tasks:

- Timestamps of foot pedal use by the participant
- Retrospective recall of total elapsed time
- Time to complete task/progress at experiment end
- Question responses

Following completion of the tasks the data collected can be analysed as below.

Time interval analysis:

- Intervals between pedal presses are extracted for each scenario (timing control/administrative/technical tasks)
 - Derive: min/max/mean/interquartile range/standard deviation for each case
- Comparison of the individual’s retrospective perceived elapsed time with actual elapsed time. Reported as percentage error of actual elapsed time.

This will allow the following results to be reported:

- Mean deviation for each individual from their baseline in each of the tasks.
- Change in retrospective perceived elapsed time compared to actual elapsed time.
- Distribution of timing in the control task for each individual.
- Paired t-test comparison to test if there are significant differences in time interval distribution for each individual between control, administrative and technical tasks.
- Overall proportion of participants showing significant deviation from their own baseline in each of the administrative and technical tasks
- Population limits/mean
- Comparison of the mean perceived time interval between subgroups
 - By task order

- By time within task (split into thirds- 2 minutes each)
- By grade
- By number of CVCs previously inserted
- By first 25% vs last 25% of participants

Monitor trend perception analysis:

Each participant will provide question answers from immediately after the second task.

This will allow the following results to be reported:

- Rationale
 - The first question “Did you see anything of note on the monitor” is chosen to highlight inattentive blindness and is asked immediately to avoid any impact from the role of memory or priming from other questions asked.
 - This will be reported as proportion who noted a change
 - The subsequent questions are asked to elicit responses from those who observed the trend but are not sufficiently confident in their recall to report it.
- From the responses the following can be derived:
 - Correct identification of the blood pressure trend- reported as proportion of participants correct

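### The timing control always runs first, so the control-versus-task tests and the deviation-from-baseline results mix task load with position and pedal practice; administrative versus technical is protected

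*Combined protocol and SAP*

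**What the plan says.** The Experimental scenarios section fixes the sequence: "Each participant will undertake the timing control task first and then both the administrative and technical tasks, the order of these determined by the randomisation". The Structure table gives the control's purpose as measuring each participant's baseline time perception. It lasts 6 minutes and is followed by a break of unstated length.

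The Randomisation section names two randomised elements. One is the monitor scenario. The other concerns order: "The first is the order in which the administrative and technical tasks are performed". The reason given is "this is randomised to remove the impact of primacy-recency impacts as well as task training through more practice with the timing apparatus".

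Statistical methods plans a "paired sample t-test for; control vs administrative, control vs technical and administrative vs technical". The Time interval analysis section adds "Mean deviation for each individual from their baseline in each of the tasks" and "Overall proportion of participants showing significant deviation from their own baseline in each of the administrative and technical tasks". It also lists subgroup comparisons of the mean interval by task order and by thirds of a task.

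The Hypothesis section states the timing alternative, H_A, as technical against administrative. The control does not appear in it.

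**The concern.** The protocol treats position and practice with the pedal as real enough threats to randomise against. It applies that protection to one of its three timing contrasts and leaves the other two exposed. Control data always come from a participant's first minutes on the pedal. Task data always come later, after about 36 presses if intervals are near the 10-second target (360 s / 10 s).

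A difference between control and either task could therefore reflect load, practice, fatigue, drift over the session, or a mixture. The Introduction says the paired testing is meant to show whether task loading affects accuracy, and a significant control-versus-task difference would naturally be taken as evidence of that. The Outcomes and significance section links impaired time perception to the need for an assistant and to policy change, so the attribution matters even in a pilot.

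**Working it through.** **Inputs from the protocol.** The control is in position 1 for all participants, and the two tasks occupy positions 2 and 3 in randomised order. The appendix list has 20 entries per stratum. Counting them gives 10 administrative-first and 10 technical-first among consultants, and the same among others, with 2:2 in every block of four. The plan states no sample size, drift or SD, so there is no figure of its own to reproduce.

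**Position terms.** Let p1, p2 and p3 be the effects of positions 1, 2 and 3 on a participant's timing summary, and let C, A and T be the effects of control, administrative and technical. With half of participants in each order, the expected values are:

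- control: C + p1
- administrative: A + (p2+p3)/2
- technical: T + (p2+p3)/2

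The three planned contrasts are then:

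- administrative - control = (A - C) + (p2+p3)/2 - p1
- technical - control = (T - C) + (p2+p3)/2 - p1
- technical - administrative = T - A, with no position term

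The difference between the two baseline deviations is (technical - control) - (administrative - control) = T - A. It is the same protected contrast.

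**Two shapes for the extra term.** Under linear drift of d per block (p2 = p1 + d, p3 = p1 + 2d), the term is (d + 2d)/2 = 1.5d. Under a single shift s after first exposure, then a plateau (p2 = p3 = p1 + s), the term is s. In both cases technical vs administrative is unbiased over complete blocks.

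**Why the planned checks do not help.** The by-task-order comparison sets position 2 against position 3. The thirds comparison looks within a block. Neither contains p1 apart from the control, because position 1 is always the control. Projecting a p2-to-p3 trend back to p1 would require assuming its shape, and practice may well plateau.

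**Illustration only.** Every input here is assumed: linear drift, SD of paired differences 1.5 s, two-sided 5% test, no load effect, and n of 20 or 40 (the protocol gives only a recruitment pool of around 40). The noncentrality is 1.5d / (SD/√n). For n = 40 and d = 0.3 s it is 0.45 / (1.5/6.325) = 1.90.

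| d per block | bias in each control contrast | rejection, n = 20 | rejection, n = 40 |
|---|---|---|---|
| 0.1 s | 0.15 s | 7% | 9.5% |
| 0.2 s | 0.30 s | 14% | 24% |
| 0.3 s | 0.45 s | 25% | 46% |

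At d = 0.3 s, moving the SD from 1.0 to 2.5 s takes rejection from 48% to 12% (n = 20) and from 79% to 20% (n = 40). A separate simulation of all three tests, with no task effect and position shifts of 0 to 0.5 SD per step, kept technical vs administrative at 3-5% throughout.

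The bias can also run the other way. A true load effect of +0.45 s with d = -0.3 s gives an expected difference of 0.45 - 0.45 = 0, so the test would reject only at its nominal 5%.

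**The case against.** The strongest reply is that the study's stated inference is already safe. H_A and the objective concern two types of task, that comparison has randomised order, and the list is balanced. This stands. A reader might infer that the main timing hypothesis is compromised, but the protocol does not support that. The protection is at group level only, since each individual has one fixed order. The monitor-trend outcome does not use the control and is not affected.

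It can also be said that this is a pilot, described as hypothesis generating and not powered to confirm. That lowers the stakes, but the control contrasts are still planned significance tests, and the plan carries no caution about them.

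A third reply is that a baseline belongs first and gives everyone the same pedal exposure before the scored tasks. This is a real merit, and it is why the point should not be stretched into a call to move the control or randomise its position. Doing so would remove that uniform exposure for some participants, add first-use noise to the contrast that tests H_A, and place some baselines after both loaded tasks.

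A reader might extend the point to the recalled total elapsed time, on the view that the question is unexpected only after the control. The documents do not support that. They specify no control contrast for this estimate, which is reported as percentage error against actual elapsed time. The Background distinguishes retrospective from prospective judgement, not expected from unexpected questions. The information sheet is not in the available text, so surprise cannot be shown.

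**Conclusion.** The point holds for the control-versus-administrative and control-versus-technical tests, the mean deviation from baseline in each task, and the proportion deviating from baseline. Each mixes task load with position and practice, and no planned analysis can separate them. The unwanted term is (p2+p3)/2 - p1, of unknown sign and size. That result needs only additive position effects and balanced order.

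The rejection rates should not be read as this study's actual error rates. They rest wholly on assumed drift, SD and n, and they show only the false-positive side. Administrative vs technical, and equally the difference between the two baseline deviations, remains sound at group level. This is a correctable limit on interpretation, worth making before results are reported.

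**What to change.** In Time interval analysis and Statistical methods, state that conclusions about task loading and time perception rest on the order-randomised administrative-versus-technical contrast, or equivalently on the difference between the two baseline deviations. State that the two control-versus-task comparisons, the mean deviation from baseline in each task and the proportion deviating from baseline are reported descriptively, because the control always comes first and they are confounded with order.

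This changes wording only: no procedure, allocation list or data collection is altered. The downside is that two of the three planned timing tests lose inferential status.
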